## Subgroup analyses

Subgroup analyses are planned to explore a possible heterogeneity of the treatment effect concerning the following baseline characteristics: setting (outpatients versus hospitalized patients), gender (male, female, diverse), age (< 65 versus  $\geq$  65 years), kidney function (eGFR  $\geq$  30 mL/min/1.73m^2 and < 50 mL/min/1.73m^2 versus eGFR  $\geq$  50 mL/min/1.73m^2), smoking status, diabetes, presence of coronary heart disease or heart failure (yes/no), need for oxygen treatment at baseline (supplementary oxygen required versus not required), inclusion based on D-dimer, hs-cTnT or both. For subgroup analyses the respective baseline characteristic and its interaction with treatment are included in the regression

models described above for the primary and secondary endpoints. Treatment effect heterogeneity across subgroups will also be visually inspected in forest plots.

### **Safety Endpoints**

Safety analyses will follow standard procedures for the reporting of adverse events; these will be reported as frequencies (percentages) by treatment group. All safety analyses will be based on the safety set. One safety endpoint of particular interest are bleeding events (see Section 9.3.1). The time to bleeding events will be analyzed in a Cox proportional hazards model, if a sufficient number of events will be observed. Treatment group differences will be reported as hazard ratios with 95% confidence intervals and p-values testing the null hypothesis of no group difference (i.e. HR=1). The estimation of the probability for bleeding events will account for competing events such as death and premature study discontinuation using the Aalen-Johansen estimator, the so-called cumulative incidence function.

Differences between treatment groups in continuous laboratory parameters and vital signs over follow-up time will be explored in longitudinal box plots.

## TIME AND EVENTS SCHEDULE

Period	Screening a	Randomization	Therapeutic anticoagulation		Prophylactic anticoagulation	Follow-up
			Day 7	Discharge b		
Visit	Screen	Rand	Day 7	Discharge b	Endpoint visit	EOS visit c
Days from randomization		0	7	Discharge day (variable)	35 days post Rand	60 days post Rand
Day window	-3/ 0	0	-2/ +1	-2/ 0	-0/+5	-3/+4
Informed consent	X					
Inclusion/Exclusion d	X	X				
SARS-CoV-2 test + e	X					
Physical Exam and Vitals f	X		X	X	X	(X)
D-dimer g,h	X		X	X	X	(X)
hs-cTnT g,h	X					
Demographics	X					
Medical History	X					
Hemoglobin/Platelet count g	X		X	X	X	
Serum creatinine g	X		X	X	X	
Serum/urine Pregnancy i	X					
Further safety blood assessment j	X		X		X	
ECG	X		X	X	(X)	
Registration		X				
Dispense Study Drug		X	X	X		
Study drug accountability			X	X	X	
Adverse Events		X	X	X	X	X
CTPA k			(X)	(X)	(X)	
Seven-category ordinal scale			X	X	X	X
Endpoint assessment			X	X	X	X
Concomitant Medications	X	X	X	X	X	X
Blood sampling l		(X)	(X)	(X)	(X)	(X)

EOT= end of treatment; EOS = end of study; hs-cTnT= high sensitive cardiac troponin T; ECG= electrocardiogram; CTPA= Computed tomography pulmonary angiogram

- The time between the confirmation of a positive SARS-CoV-2 test and screening should not exceed 14 days.
- If the patient is discharged later than day 10 post randomization a discharge visit becomes mandatory.
- This visit may be performed as telephone visit.
- Screening inclusion / exclusion criteria should be assessed and verified at randomization.
- The subject might be eligible for the study, if the SARS-CoV-2 polymerase chain reaction (PCR) test had been positive within 14 days prior to randomization. There is no need to repeat the SARS-CoV-2 PCR test in the screening period.

- f. Vital signs include pulse, blood pressure, temperature, respiratory rate and oxygen saturation.
- g. Hemoglobin, platelet count, serum creatinine, D-dimer, hs-cTnT and white blood cell differential will be obtained by the local laboratory.
- h. D-dimer and hs-cTnT values from up to 3 days prior to screening can be used.
- i. Pregnancy test must be performed in women of child-bearing potential.
- j. Further safety blood assay comprises aspartate aminotransferase (AST), alanine aminotransferase (ALT), international normalized ratio (INR), activated partial thromboplastin time (aPTT), high sensitive C reactive protein (hs-CRP), NT-pro-BNP and should be done by local laboratory.
- k. A CTPA is highly recommended if the patient has severe symptoms or deteriorates.
- l. Possible blood sampling for bio-banking: Serum, heparin, citrate and Ethylendiamintetraessigsäure (EDTA) blood for coagulation analysis and molecular analysis (not mandatory). Samples should be sent to Charité Campus Benjamin Franklin.

## ABBREVIATIONS

aPTT	activated Partial Thromboplastin Time
ALT	alanine aminotransferase
AST	aspartate aminotransferase
AT	arterial thromboembolism
CAD	coronary artery disease
CKD-EPI	Chronic Kidney Disease Epidemiology Collaboration
CEC	Clinical Event Committee
CI	Cardiac index
CI	confidence interval
COVID-19	coronavirus disease 2019
CT	computed tomography
CTPA	computed tomography pulmonary angiogram
CV	cardiovascular
CYP3A4	Cytochrome P450 3A4
DIC	disseminated intravascular coagulation
DSMB	data safety monitoring board
DVT	deep vein thrombosis
eGFR	estimated glomerular filtration rate
eCRF	electronic case report form
eDC	electronic data capture
EDTA	Ethylendiamintetraessigsäure
EC	Executive Committee
ECG	electrocardiogramm
EOS	end of study
EOT	end of treatment
ESC	European Society of Cardiology
EU	European Union
FXa	factor Xa
FXIa	factor XIa
GCP	Good Clinical Practice
HR	hazard ratio
hs-TnT	high sensitive cardiac troponin T
hsCRP	high sensitive C reactive protein
ICF	informed consent form
ICH	International Conference on Harmonisation
ICU	intensive care unit
IEC	Independent Ethics Committee
INR	international normalized ratio
IRB	Institutional Review Board
ISTH	International Society on Thrombosis and Haemostasis
ITT	intention-to-treat
i.v.	intravenous
LMWH	low molecular weight heparin
MI	myocardial infarction
NOAC	non vitamin K antagonist oral anticoagulants
NT-pro-BNP	N-terminal prohormone of brain natriuretic peptide
OD	once daily
PAD	peripheral artery disease
PCR	polymerase chain reaction
PE	pulmonary embolism
P-gp	combined P-glycoprotein
PQC	product quality complaint
SARS-CoV-2	severe acute respiratory syndrome coronavirus 2
s.c.	subcutaneous
SmPC	summary of product characteristics
SOC	standard of care
SUSAR	suspected unexpected serious adverse reaction
TSAT	transferrin saturation
UFH	unfractionated heparin
ULN	upper limit of normal

VTE            venous thromboembolism  
V-Q            ventilation-perfusion  
WHO           world health organization

# 1. INTRODUCTION

Rivaroxaban is an oral, direct acting, FXa inhibitor anticoagulant that has been under development for the treatment of several thrombosis-mediated conditions. Rivaroxaban is marketed under the trade name XARELTO® and has been approved for multiple indications in more than 130 countries. The clinical development program for rivaroxaban is extensive. Over 100,000 subjects have been studied from Phase 1 through multiple large Phase 4 studies, covering several indications and potential indications in the overall clinical development program. Subjects have been exposed to rivaroxaban in interventional clinical trials and non-interventional studies, with the total daily doses of rivaroxaban ranging between 5 mg and 60 mg.

Rivaroxaban has been approved for the reduction in the risk of stroke and systemic embolism in patients with non-valvular atrial fibrillation, for the treatment of DVT and PE, for the reduction in the risk of recurrence of DVT and/or PE in patients at continued risk for recurrent DVT and/or PE after completion of initial treatment lasting at least 6 months, and for the prophylaxis of DVT, which may lead to PE in patients undergoing knee or hip replacement surgery. Moreover, it has been used in combination with aspirin, to reduce the risk of major cardiovascular events (cardiovascular (CV) death, MI and stroke) in patients with chronic CAD or peripheral artery disease (PAD)(1-3).

## 1.1. Background

The ongoing pandemic of COVID-19, caused by SARS-CoV-2 is associated with significant cardiovascular morbidity and mortality as the number of infected cases is increasing world-wide. The majority of moderate to severely ill patients initially present with respiratory failure, and may progress to a systemic disease associated with markedly increased risk of thromboembolism, DIC and CV events, as observed already in China, Italy and also Germany (4) (5, 6).

A significant clinical feature of poor prognosis in these patients is the development of a prothrombotic state. It has previously been observed that in patients who develop sepsis from various infectious agents, occurrence of a prothrombotic state is a major predictor of a poor clinical outcome (7). This premise has been confirmed in different studies in patients with COVID-19 infection, in whom a coagulation dysfunction is present (6) (8, 9) (10) and is associated with a poor prognosis (9). In a multicenter retrospective cohort study, an elevated D-dimer ( $> 1000\mu\text{g/L}$ ) was associated with in-hospital death (OR 18.42, 95% CI 2.64-128.55,  $p=0.0033$ ) (11).

The rate of thromboembolic events in patients with severe COVID-19 infection has been observed to be substantially increased. A study conducted in two hospitals in the Netherlands found a cumulative incidence of thromboembolic events of 31% (95% CI 20-41%) in patients treated on the ICU (12). The incidence of peripheral thromboembolism in patients with severe COVID-19 has been observed to vary between varies from 25 to 69% (13). In a retrospective study in patients with severe COVID-19, a cumulative incidence of peripheral VTE of 69% was found, being 100% in patients with prophylactic anticoagulation in comparison to 56% in patients with therapeutic anticoagulation (14). Regarding DIC, it has been observed that it occurred in 71% of patients who did not survive the infection compared to DIC occurring in  $<1\%$  of patients who survived the infection (9).

In line with these observations, autopsies of patients with severe hypoxemia confirmed multiple primary pulmonary thrombi and emboli (15). That has also been observed in autopsies at the Charité University Hospital and the University Hospital of Hamburg (approximately 30% pulmonary emboli/thrombosis in COVID-19, unpublished observations). Therefore, in some center's empirical application of systemic anticoagulation as aiming to protect these patients against thromboembolism. Chinese colleagues from the Tongji hospital have retrospectively compared the 28-day mortality between heparin users and non-users in patients with severe COVID-19. Anticoagulant heparin therapy was associated with a better prognosis in patients with severe COVID-19 (16). The 28-day mortality was lower in heparin users compared to non-users in the subgroup of patients with a sepsis-induced coagulopathy score  $\geq 4$  (40.0% vs 64.2%,  $P=0.029$ ), and in the subgroup of patients with a D-dimer  $>6$ -fold ULN (32.8% vs 52.4%,  $P=0.017$ ) (16). These findings point to the importance of a preventive anticoagulation therapy for improving clinical outcomes in specific high-risk subgroups of patients with COVID-19.

Additionally, several studies suggest an association between cardiovascular disease (CVD) and COVID-19, being the presence of these previous conditions also associated with severe disease and mortality (17) (18). A significant proportion of patients with COVID-19 develop acute cardiac injury during the course of the disease. Acute cardiac injury, defined as significant elevation of cardiac troponins, is the most commonly reported cardiac abnormality in COVID-19. It occurs in  $>10\%$  of all hospitalized patients. In a meta-analysis of 4 studies with 341 patients, a significant difference of the troponin serum

levels was seen between patients with severe disease in comparison to those with milder disease (delta of 25.64, 95% CI 6.76-44.53, p=0.001) (19).

Although little is known about cardiovascular manifestations in COVID-19, it has become overt that the development of acute cardiac injury significantly worsens the clinical outcome in these patients (20), including the development of thromboembolic events and myocardial infarction.

Taking all these data into account, together with COVID-19-associated systemic inflammation, coagulation activation, hypoxemia and immobilization of the patients upon hospital admission, the actual ESC guidance for the diagnosis and management of cardiovascular disease during the COVID-19 pandemic recommends anticoagulation at standard prophylactic doses for all patients admitted to the hospital with COVID-19 infection (26). Due to the lack of data, it is currently not known whether anticoagulation at therapeutic doses is superior to prophylactic anticoagulation in patients with moderate to severe COVID-19.

Of note, some of the investigational drugs for COVID-19 may have relevant drug-drug interactions with NOACs. In particular, this may be the case for lopinavir/ritonavir due to Cytochrome P450 3A4 (CYP3A4) and/or P-glycoprotein (P-gp) inhibition. In such cases, the bleeding risk may be elevated and NOACs should be avoided. The ESC guidance position points out that severely ill COVID-19 patients should be switched to parenteral anticoagulation, which has no clinically relevant drug-drug interactions with specific COVID-19 therapies. In contrary, no interactions have been described so far for remdesivir and NOACs. Remdesivir has recently received an authorization from the European Commission as first COVID-treatment due to the urgency of the COVID-19 pandemic.

Data from several large prospective randomized clinical trials showed that oral anticoagulation with the direct factor FXa inhibitor, rivaroxaban, prevents not only thromboembolic events in patients with previous VTE, but also reduces major adverse cardiovascular event rates in patients with coronary artery disease. Moreover, factor XIa (FXIa) has become a target for new anticoagulants that appears to be safer than those available now. Phase 2 studies that assess the effect of FXIa inhibitors on clinical outcomes are currently ongoing.

Regarding the lack of data considering anticoagulant therapy in patients with COVID-19, it is crucial to perform prospective randomized trials to substantiate the above-mentioned potential major benefits derived from anticoagulation in these patients. This study is one of the first that compares therapeutic with prophylactic anticoagulation and addresses the role of a NOAC as a potential anticoagulant for COVID-19.

### **1.1.1. Compound Profile**

As part of the prothrombinase complex, FXa directly converts prothrombin to thrombin. Thrombin converts fibrinogen to fibrin and activates platelets leading to clot formation. FXa occupies a critical place in the coagulation cascade since it is at the confluence of both the intrinsic and extrinsic clotting pathways and is the key amplification point for the generation of thrombin. One molecule of FXa is able to generate more than 1,000 molecules of thrombin due to the amplification nature of the coagulation cascade. Selective inhibitors of FXa can terminate the amplified burst of thrombin generation and prevent clot formation.

Rivaroxaban is an oral, direct, FXa inhibitor anticoagulant. Rivaroxaban is rapidly absorbed after oral administration, with peak plasma concentrations occurring approximately 2 to 4 hours post dose. The elimination pathways of rivaroxaban include both hepatic and renal routes. The terminal elimination half-life of rivaroxaban is 5 to 9 hours in healthy young subjects and from 11 to 13 hours in healthy elderly subjects (aged 65 to 83 years). Due to the multiple elimination pathways of rivaroxaban, there are few clinically relevant drug-drug interactions.

## **1.2. Overall Rationale for the Study**

The primary objective is to assess the effect of rivaroxaban compared with standard of care (SOC) with the use of prophylactic low molecular weight heparin (LMWH) or unfractionated heparin (UFH) (see Attachment 1) on D-dimer as a clinical marker for the clinical outcome at day 7 post randomization adjusted for baseline measurement in patients with moderate to severe COVID-19.

The secondary objectives are to assess the efficacy and safety of rivaroxaban compared with standard of care (SOC) with the use of prophylactic low molecular weight heparin (LMWH) or unfractionated

heparin (UFH) in the prevention of thromboembolic events, cardiovascular events, all-cause death or progression to intubation and invasive ventilation up to day 35 in patients with moderate to severe COVID-19.

Previous studies assessed the efficacy and safety of rivaroxaban, compared with SOC in the prevention of symptomatic VTE (lower extremity DVT and non-fatal PE) and VTE-related death (death due to PE or death in which PE cannot be ruled out as the cause) during hospital stay and post-hospital discharge in high-risk medically ill subjects.

The MAGELLAN study failed to demonstrate a positive benefit/risk profile for extended duration thromboprophylaxis in patients hospitalized for acute medical illness, primarily due to excessive bleeding with the anticoagulants (21). However, a subgroup analyses presented as a Forrest plot in the appendix indicated that rivaroxaban 10 mg OD was superior over LMWH/placebo in elderly patients, those suffering from respiratory insufficiency and those affected by infectious or inflammatory diseases, highlighting the patient profile seen in COVID-19. Furthermore, a post-hoc analysis identified elevated D-dimers on admission as a biomarker that indicates patients who would benefit from extended rivaroxaban prophylaxis.

The MARINER study was then designed to improve the overall safety of medically ill patients with rivaroxaban treatment for 45 days post hospital discharge by addressing the bleeding risk observed in the MAGELLAN study. The MARINER patients exhibited a higher VTE-risk than those in MAGELLAN to enhance the overall expected benefit/risk assessment (22). The VTE-risk in the patients from the MARINER Study was more than 2,9% annually according to the IMPROVE Score. The study did not show a benefit in reducing the risk of the composite endpoint (VTE and VTE related death) in acute medically ill patients following hospital discharge. However, when examining VTE only, fewer events were observed in the group treated with rivaroxaban. The incidence of major bleeding in both study arms was low.

According to the actual literature, patients with COVID-19 present a much higher incidence of thrombotic complications than those included in the MARINER study, even with prophylactic anticoagulation (12, 14). Therefore, COVID-PREVENT was designed to determine whether the use of rivaroxaban at a dose of 20mg OD combined with a thromboprophylaxis dose of 10mg OD post discharge reduces fatal or nonfatal thromboembolic and cardiovascular events in comparison to SOC with prophylactic LMWH or UFH in patients with moderate to severe COVID-19.

## **2. OBJECTIVES AND HYPOTHESIS**

### **2.1 Objectives**

#### **Primary Objective**

The primary objective is to assess the effect of rivaroxaban compared with standard of care (SOC) with the use of prophylactic low molecular weight heparin (LMWH) or unfractionated heparin (UFH) (see Attachment 1) on D-dimer as a clinical marker for the clinical outcome at day 7 post randomization adjusted for baseline measurement in patients with moderate to severe COVID-19.

The co-primary objective is to evaluate the impact of rivaroxaban compared with standard of care (SOC) with the use of prophylactic low molecular weight heparin (LMWH) or unfractionated heparin (UFH) on a seven-category ordinal scale recommended by the WHO as a measure of clinical benefit at day 7 post randomization adjusted for baseline score in patients with moderate to severe COVID-19.

#### Primary Endpoint

- D-dimer at day 7 post randomization

#### Co-primary Endpoint

- Seven-category ordinal scale recommended by the WHO at day 7 post randomization (Attachment 2)

## Secondary Objectives

The secondary objectives are to assess the efficacy and safety of rivaroxaban compared with standard of care (SOC) with the use of prophylactic low molecular weight heparin (LMWH) or unfractionated heparin (UFH) in the prevention of thromboembolic events, cardiovascular events, all-cause death or progression to intubation and invasive ventilation up to day 35 in patients with moderate to severe COVID-19.

### Secondary combined Endpoint

Time to first event of either of

- Venous thromboembolism (VTE) (deep venous thrombosis (DVT) and/or fatal or non-fatal pulmonary embolism (PE))
- Arterial thromboembolism
- New myocardial infarction (MI)
- Non-hemorrhagic stroke
- All-cause death
- Progression to intubation and invasive ventilation

In addition, the components VTE, arterial thromboembolism, MI, non-hemorrhagic stroke and all-cause-death of the secondary endpoint will be additionally evaluated, if sufficient numbers of events are observed.

Furthermore, all single components of the secondary composite endpoints will be additionally evaluated separately, if sufficient numbers of events are observed.

## Safety Objectives

The safety objectives are to compare rivaroxaban with SOC with prophylactic LMWH or UFH in bleeding outcomes up to day 35 in patients with moderate to severe COVID-19.

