### Primary Safety Endpoints:

- Fatal and non-fatal major bleeding using the International Society on Thrombosis and Haemostasis (ISTH) bleeding criteria

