### 3. STUDY DESIGN AND RATIONALE

#### 3.1 Overview Study Design

This is a multicenter, prospective, randomized, event-driven phase II study designed to assess the effect of therapeutic anticoagulation with high dose rivaroxaban intended for at least 7 days compared with SOC with prophylactic LMWH or UFH on the clinical prognosis marker D-dimer at day 7 post randomization adjusted for baseline measurement in patients with moderate to severe COVID-19. Moreover, this study investigates the effect of therapeutic anticoagulation with rivaroxaban compared with SOC with prophylactic LMWH or UFH on a seven-category ordinal scale for patients with respiratory infections at day 7 post randomization adjusted for baseline score.

Secondarily, this trial is designed to evaluate therapeutic anticoagulation with rivaroxaban for at least 7 days followed by thromboprophylaxis with rivaroxaban for 28 days, as compared with SOC with prophylactic LMWH or UFH in the prevention of the composite of VTE (DVT and/or fatal or non-fatal PE), arterial thromboembolism, new MI, non-hemorrhagic stroke, all-cause death and progression to intubation and invasive ventilation up to day 35 post randomization in patients with moderate to severe COVID-19. The study consists of a screening phase, a therapeutic treatment phase of at least 7 days and a thromboprophylaxis phase up to day 35 post randomization. The physicians of the respective trial site decide which heparin, of the heparins approved in Germany, the patients assigned to treatment group "SOC with prophylactic UFH or LMWH" will receive.

The subject population comprises men and women aged 18 years and older who have been tested positive for SARS-CoV-2 and who have moderate to severe COVID-19.

In order to be eligible, all patients must exhibit at least one of the following conditions:

- D-dimer elevation > 1.5 ULN (using age-adjusted cut-offs) and/or
- Cardiac injury reflected by an elevation in hs-cTnT > 2.0 ULN and one of the following conditions:
  - Known CAD
  - Known diabetes mellitus
  - Active smoking

The inclusion of D-dimer negative patients with cardiac injury reflected by an elevation in hs-cTnT > 2.0 ULN and one of the following conditions, known CAD or known diabetes mellitus or active smoking, will be limited to 15 % of the patients included in the study.

85% or more of the patients enrolled should be enrolled due to increased D-dimer defined as:

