In case of hospitalization for more than 7 days, the therapeutic treatment with rivaroxaban will be continued for the duration of the hospital stay until discharge. After at least 7 days of therapeutic treatment with rivaroxaban or after hospital discharge, whatever is the event that occurs later, the study dose of rivaroxaban will be adjusted as follows: Patients randomized to rivaroxaban 20mg OD will reduce daily dosage to 10 mg OD, provided that they were not diagnosed with a condition requiring continued therapeutic anticoagulation. Thromboprophylaxis therapy will be given for 28 days up to day 35 post randomization or even longer. If the patient cannot be discharged from the hospital prior to day 35 post randomization, the thromboprophylaxis phase will also start upon hospital discharge, but is then shorter than 28 days, because the study ends latest at day 60 post randomization. The complete end of study (EOS) visit will be done via phone call 60 days post randomization. No study medication will be given thereafter.

After the study, the patients continue to receive medical therapy according to local practice.

If the clinical condition of a hospitalized patient deteriorates and admission to ICU with possible invasive ventilation will become necessary, treatment with rivaroxaban should be discontinued for the ICU period and the patient switched to parental or subcutaneous anticoagulation following best local practice. After clinical improvement and discontinuation of invasive ventilation, the anticoagulation mentioned above can be replaced by study drug rivaroxaban 20 mg OD (15 mg for subjects with an  $eGFR \geq 30$  mL/min/1.73m^2 and <50 mL/min/1.73m^2) at the discretion of the clinically responsible physician.

Patients randomized to the SOC treatment arm will receive SOC during the time of hospitalization or for at least 7 days, whatever is later. SOC constitutes of prophylactic doses of LMWH or UFH, according to the local practice and decision of the physicians of the respective trial site. Study visits are terminated 7, 35, and 60 days post randomization in all patients. The latter will be done via phone call if applicable. For the hospitalized patients who are discharged later than 10 days post randomization, an additional discharge visit will be done at the day of discharge (-2 days).

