Throughout the study, study drug will be dispensed at appropriate intervals (see the TIME AND EVENTS SCHEDULE) to ensure that subjects have adequate quantities of study drug between study visits. After at least 7 days of therapeutic treatment with rivaroxaban or after hospital discharge, whatever is the event that occurs later, the study dose of rivaroxaban will be adjusted as follows: Patients randomized to rivaroxaban 20 mg OD (15 mg OD in case of renal impairment) will reduce daily dosage to 10 mg OD, provided that they were not diagnosed with a condition requiring continued therapeutic anticoagulation. Thromboprophylaxis in the rivaroxaban arm will be given for the duration of 28 days, but not longer than 60 days post randomization.

If a patient that at the time of randomization into the rivaroxaban arm has been an out-patient is hospitalized a therapeutic anticoagulation with rivaroxaban 20 mg OD (15 mg OD in subjects  $eGFR \geq 30$  mL/min/1.73m^2 and  $< 50$  mL/min/1.73m^2) should be performed during hospital stay.

If the subject is hospitalized for more than 60 days post randomization, anticoagulation will be given according to the local standards. However, chronic therapy with the study drug is not being tested. For these reasons, rivaroxaban will not be provided to the subject after the subject completes the EOT visit 60 post randomization unless required by local regulations. It will only be after data from the entire study is analyzed that it will be determined if the population at risk will benefit from treatment.

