## 7. TREATMENT COMPLIANCE

Subjects will return empty study drug containers and unused study drug when a new supply of study drug is to be received. The last dose of study drug should not be taken later than 60 days post randomization. Subjects will also return their study drug containers and unused study drug at the EOT visit. Study drug accountability will be performed as indicated in the TIME AND EVENTS SCHEDULE.

Subjects should report any intentional or unintentional interruption or missed doses to the study site personnel at each visit.

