### **Follow-up**

#### EOS Visit (60 days post randomization)

EOS visit will be conducted as a telephone visit, but – if the patient is still hospitalized - can also be done at the clinic. Adverse events will be collected as specified in Section 12, outcome assessment will also be performed, and information about concomitant medication will be collected as specified in Section 8. Subject counseling provided at the randomization, and in hospital visits will be again repeated in detail:

- The need to seek for medical attention if any of the symptoms of above-mentioned diseases are developed
- The need to inform the treating health care providers about study participation
- The need to inform the investigator as soon as symptoms develop

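### The safety objective compares bleeding only to day 35, but scheduled rivaroxaban runs past day 35 for every patient discharged after day 7

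*Protocol*

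**What the plan says.** The safety objective, in the Synopsis and again in section 2.1, is to compare rivaroxaban with standard of care (SOC) "in bleeding outcomes up to day 35 in patients with moderate to severe COVID-19". The principal safety endpoint listed beneath it, "Fatal and non-fatal major bleeding using the International Society on Thrombosis and Haemostasis (ISTH) bleeding criteria", has no time window of its own. Section 9.3.1 (bleeding definitions) and section 11.5 (Cox model and cumulative incidence of bleeding) also give none. Day 35 in the objective is thus the only window stated for the bleeding comparison.

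The end of rivaroxaban is described in more than one way:

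- Section 3.1 first speaks of "a therapeutic treatment phase of at least 7 days and a thromboprophylaxis phase up to day 35 post randomization". The design overview in the Synopsis also ends this phase at day 35.
- Section 3.1 then says that, in stays beyond 7 days, "the therapeutic treatment with rivaroxaban will be continued for the duration of the hospital stay until discharge", and that "Thromboprophylaxis therapy will be given for 28 days up to day 35 post randomization or even longer".
- Section 6 says "Thromboprophylaxis in the rivaroxaban arm will be given for the duration of 28 days, but not longer than 60 days post randomization".
- Section 7 says "The last dose of study drug should not be taken later than 60 days post randomization".

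For SOC, section 3.1 gives prophylactic heparin for the hospital stay or at least 7 days, whichever is later. The Synopsis leaves SOC heparin around discharge to local practice.

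Follow-up runs to day 60 (section 10.1). For the end-of-study contact, section 9.1.3 states "Adverse events will be collected as specified in Section 12, outcome assessment will also be performed". The Time and Events Schedule marks adverse events and endpoint assessment at that visit, and section 12.1.3 records adverse events to the end of follow-up.

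**The concern.** Day 35 is 7 days of therapeutic treatment plus 28 days of prophylaxis. It describes a patient who changes dose on day 7. The protocol expects later changes: the discharge visit becomes mandatory when discharge falls after day 10, and study drug is dispensed at it. For such patients, the stated bleeding comparison closes while scheduled study drug is still being taken.

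Bleeding during extended treatment is a risk the protocol itself highlights. Section 1.2 says that an earlier trial of extended prophylaxis in acutely ill medical patients failed to show a favourable benefit-risk balance, mainly because of excess bleeding. A window that omits the tail of the extended phase omits part of the exposure whose safety is in question.

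The omitted exposure is also unlikely to be balanced. The rivaroxaban arm has a fixed course after discharge. Section 3.1 gives the SOC arm no matching one.

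**Working it through.** **Inputs**

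- Bleeding comparison: to day 35 (Synopsis and section 2.1, Safety Objectives).
- Therapeutic phase: to day 7 or discharge day D, whichever is later (section 3.1).
- Prophylaxis: 28 days (sections 3.1 and 6).
- Ceiling on study drug: day 60 (sections 6 and 7).

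**Formulas**

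- Last scheduled day: E = min(60, max(7, D) + 28).
- Scheduled days outside the window: max(0, E − 35). For D from 8 to 32 this equals D − 7.
- Share outside: (E − 35) / E, counting the scheduled course as E days.

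**The plan's own figure.** For D ≤ 7, E = 7 + 28 = 35. Day 35 is reproduced, but only for patients who step down at day 7, including outpatients who stay out of hospital.

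**Later discharge**

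| Discharge day D | Last scheduled day E | Days after day 35 | Share of scheduled days |
|---|---|---|---|
| 7 or earlier | 35 | 0 | 0% |
| 8 | 36 | 1 | 3% |
| 10 | 38 | 3 | 8% |
| 14 | 42 | 7 | 17% |
| 20 | 48 | 13 | 27% |
| 28 | 56 | 21 | 38% |
| 32 or later | 60 | 25 | 42% |

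For example, D = 20 gives E = 20 + 28 = 48, then 48 − 35 = 13, and 13 / 48 = 27%. Day 60 is reached only from D = 32, because 32 + 28 = 60.

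**What the table does not show.** These are scheduled days for one patient at a chosen discharge day. They are not shares of the trial's total exposure, which would need a discharge-day distribution that the protocol does not give. They are also upper figures for rivaroxaban itself: sections 3.1, 4.3 and 10.2.2 provide for a switch to other anticoagulation during critical illness in intensive care, and those patients are likely to be among the longest stays.

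**With the window at day 60.** Because E never exceeds 60, no scheduled rivaroxaban day falls outside a comparison that runs to day 60.

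**The case against.** The strongest reply is that the cut-off stands in the objective alone. Section 9.3.1 ties bleeding evaluation to the Time and Events Schedule, which includes the day-60 visit. The adjudication committee in section 3.3.3 reviews suspected events after randomisation without a day-35 stop. A reader might infer that on-drug bleeds after day 35 are excluded from the principal safety endpoint. The documents do not say so. Such bleeds are collected, are reportable as events of special interest (section 12.2.1), and enter the adverse event tables by arm. This part of the reply stands. What remains is that the only window stated for the between-arm comparison is shorter than permitted treatment, while section 11.5 states none.

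Three other inferences go too far:

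- *That exposure after day 35 is in the rivaroxaban arm only.* SOC patients still in hospital then receive heparin, and the Synopsis allows SOC heparin around discharge by local practice. The imbalance is likely but not total.
- *That the cut can only lower rivaroxaban bleeding relative to SOC.* A common window drops late bleeds in both arms, so the relative effect could move either way. Only a tendency is arguable.
- *That the omitted time is high-dose time.* For anyone discharged by day 35, the scheduled days after day 35 are all at the reduced dose.

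It can also be said that a fixed window common to both arms, matching the efficacy composite, is a reasonable choice in an explorative study, and that a day-60 window adds up to 25 off-drug days for patients who finish at day 35. That is a fair reason to keep a day-35 estimate. It is not a reason to have no stated comparison over the full treatment period.

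**Conclusion.** The point holds as a mismatch between the window in the safety objective and the scheduled duration of treatment. Each rivaroxaban patient discharged on day D after day 7 who follows the schedule has D − 7 scheduled days outside the stated bleeding comparison. The maximum is 25 days, or 42% of a 60-day course. Patients who step down at day 7 have none.

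This rests on the schedule in sections 3.1, 6 and 7 being the one applied, and on no interruption of study drug. The number of patients affected cannot be derived from the protocol. On the stated schedules, late exposure lies mainly in the rivaroxaban arm, so a comparison stopped at day 35 would tend to understate that arm's bleeding. The size of any understatement is unknown. The data needed for a longer comparison are already collected, so the weakness is in the prespecified comparison and is cheap to correct.

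**What to change.** 1. In the Synopsis, section 2.1 and section 11.5, state that the principal and secondary bleeding endpoints are compared from randomisation to day 60 in both arms.
2. Report the day-35 estimate as a second time point read from the same cumulative incidence curve, which section 11.5 already plans.
3. Reconcile the descriptions in the Synopsis design overview and at the start of section 3.1 that end thromboprophylaxis at day 35 with the later text of section 3.1 and with sections 6 and 7, which allow it to continue. This review takes no view on which duration is right.

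The efficacy composite need not change. The cost is wording, since follow-up and outcome assessment already reach day 60. Section 18.1.1 says that no further recruitment is planned, so the window should be fixed before bleeding is compared between arms. The downside is the off-treatment time added for patients who finish by day 35, which may dilute a difference; the day-35 estimate addresses this.
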